4.4.2 Protocol Deviations

Important protocol deviations (IPDs) are defined as those deviations from the protocol likely to have an impact on the perceived efficacy and/or safety of study treatments. The impact of IPDs on the efficacy and/or safety results will be investigated by assessing the robustness of the study results and conclusions to the choice of analysis set, both including and excluding data potentially affected by IPDs.

Important protocol deviations and any action to be taken regarding the exclusion of participants or affected data from specific analyses are defined in the project-specific Protocol Deviation Specification.

For this study, the following general categories will be considered IPDs and will be summarised in the CSR:

- Deviation 1: Participants who did not meet the Inclusion criteria or met Exclusion criteria and received study treatment.
- Deviation 2: Participants assigned to treatment who received their assigned study treatment at an incorrect dose at one or more occasions.
- Deviation 3: Participant received prohibited medication during study treatment period.
- Deviation 4: Met study treatment discontinuation criteria but continued study treatment and potentially had major impact to participants' safety according to clinical judgement.

- Deviation 5: Missed visits, assessments, or treatments that, in the Investigator's opinion, were due to the COVID-19 global pandemic and there was a significant effect on EITHER completeness, accuracy, and/or reliability of the participant's data, OR the participant's rights, safety or well-being.
- Deviation 6: Data in CRF not consistent with source documents and/or discrepancies are not explained.

The number and percentage of participants with any IPD will be summarised for each IPD category based on the full analysis set (FAS). Participants with more than one deviation in the same IPD category will be counted once for that IPD category. Any participants who have deviations in more than one IPD category will be counted once in the overall summary.

A list of all protocol deviations, including those reported by monitors, will be reviewed and decisions regarding how to handle these deviations will be documented by the study team physician, clinical pharmacology scientist and statistician prior to database lock (DBL). The final classification will be made prior to database lock.

Programmable protocol deviations will be detected from the data recorded in the clinical database and will be reviewed at regular protocol deviation review meetings. At this meeting, the programmatically-derived protocol deviations will be checked to ensure that they have been correctly classified as important or not important protocol deviations.

On an ongoing basis throughout the study, monitoring notes or summaries will also be reviewed to determine any important post-entry deviations that are not identifiable via programming.

The final classification of IPDs will be made prior to DBL or data cut-off for final analysis. Any other deviations from monitoring notes or reports will be reported in an appendix to the CSR. A by-participant listing of important protocol deviations will be provided.

4.5 Analysis Populations

The following summaries will be provided:

- A summary of the number of participants in each analysis set by treatment group and overall. Exclusions from each analysis population will also be summarised by reason.

By-participant listings of participants excluded from each analysis set and the reasons for exclusion from each analysis set will be provided.

Table 3 Populations for Analysis

Analysis Populations	Description
Enrolled	All participants who sign the informed consent form.
Full Analysis Population	All participants who are randomised and receive any study drug. Participants are evaluated according to the treatment assigned at randomisation. The Full Analysis Population will be used for all analyses of demographic data, baseline characteristics and efficacy data.
Per Protocol Population	A subset of the Full Analysis Population consisting of all participants who receive the additional treatment with dapagliflozin post-Week 12 and do not violate the terms of the protocol in a way that may affect the primary efficacy endpoint significantly. All decisions to exclude participants from the Per-Protocol analysis set will be made and documented prior to the unblinding of the study.
Safety Analysis Population	All participants who are randomised and receive any study drug. Participants are evaluated according to the actual treatment they received. If a participant received a different treatment dose than randomised throughout the study, they will be analysed according to the treated dose, not the randomisation dose. If a participant received study drug from the wrong kit for only part of the treatment duration, they will be analysed according to their randomisation dose. The Safety Analysis set will be used for all safety analyses, unless otherwise specified.
Extended Safety Analysis Population	A subset of the Safety Analysis Population consisting of all participants who receive the additional treatment with dapagliflozin post-Week 12.
Ambulatory Blood Pressure Monitoring Population	All participants in the Full Analysis Population who have valid ambulatory blood pressure data for change from baseline analyses.

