4.9.3 Secondary Efficacy Variables

4.9.3.1 UACR at 12 Weeks

Urine ACR will be analysed to determine the dose-response effect of AZD5718 at 12 weeks (on current standard of care). The population of interest are randomised participants who meet all eligibility criteria and have valid non-missing urine ACR records at baseline and at least one post-treatment visit. The mean log change from baseline in urine ACR will be analysed using a mixed model for repeated measures. The summary measure being evaluated is the geometric mean reduction of urine ACR from baseline to Week 12. This will be evaluated using the same methods for the primary efficacy endpoint. The analysis will be repeated on the Per-Protocol Analysis Population.

The results of the model parameters (estimates, p-values, and 95% CIs) will be presented. The point estimate and 95% CI for the geometric mean ratio will be converted to the percentage change as follows:

$$[(\text{Geometric Mean Ratio} - 1) \times 100]$$

UACR will be summarized by treatment group and visit in terms of absolute values and changes from baseline.

The analysis will be repeated by strata (DKD without SGLT2i background, DKD with SGLT2i background, non-DKD), with the analysis model will include the fixed categorical effects of treatment, visit, and treatment-by-visit interaction, plus the continuous covariates of baseline log (urine ACR) and baseline log (urine ACR)-by-visit interaction.

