4.9.3.2 Estimated GFR

Estimated GFR will be analysed, comparing eGFR at baseline with that at 12 weeks, to determine whether there is any acute change with the introduction of AZD5718 to inform planning for a GFR slope analysis in Phase 3. This will be analysed using a by-visit ANCOVA, adjusting for DM stratification factor, treatment group and baseline eGFR. The FAS will be used for this analysis and eGFR will be evaluated on the original scale. The analysis will be repeated on the Per-Protocol Analysis Population.

The results of the by-visit ANCOVA will be presented by treatment group. A summary of change from baseline of eGFR results will be presented by treatment group and a by-participant listing provided of eGFR results at each visit. Plots of the least-squares mean by treatment group over time, and the mean eGFR over time up to follow-up visit will be presented.

An ANCOVA model will be produced for eGFR up to Week 20, analysed on the Per-Protocol Analysis set, similarly to that described above.

The analysis will also be repeated by strata (DKD without SGLT2i background, DKD with SGLT2i background, non-DKD), adjusting for treatment group and baseline eGFR.

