4.14 Changes in the Conduct of the Study or Planned Analysis

Following the results from the interim analysis, it was decided to terminate the study early and reduce the scope of analysis. This decision led to the removal of the MCP-Mod analysis as outlined in the protocol, and the previously described sensitivity analysis for the ABPM analysis. The statistical analysis plan has been updated to include only the analysis which will be performed following database lock.

Pharmacokinetic analyses of AZD5718 and dapagliflozin were also removed from the final analysis. The statistical analysis plan has been updated to reflect this.

Due to the early termination of the study, the total number of randomised participants is 613 with 340 participants completing treatment. Therefore, efficacy analyses should be evaluated with caution due to lack of power.

The total study duration, as highlighted in Section 3.1, will vary following study termination, up to a maximum of 28 weeks.

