Concomitant medications	X	X	X	X	X	X	X	X	X	X	X

- a Any participant with urine ACR < 30 mg/g at Week 12 will be excluded from Treatment Period 2. The eligibility check to enter Treatment Period 2 will be done at Visit 7 (Week 12) using the last available urine ACR result, calculated as the geometric mean of the replicated measurements using 3 sequential first morning urine voids.
- b Full physical examination will be completed at the indicated visits, with the exception that height will only be recorded at Screening Visit 1.
- c Serum hCG, FSH, and LH tests, and a urine dipstick pregnancy test are required for all women.
- d Except for Screening Visit 1, participants should be requested to be in a fasting state (except water) for at least 8 hours prior to sample collection and samples should be collected in the morning.

Parexel International

AstraZeneca

Statistical Analysis Plan

- e To include thyroid function tests (TSH, fT4 and fT3).
- f All vital signs (blood pressure, heart rate, respiratory rate, body temperature and pulse oximetry) will be measured with the participant in a supine position having rested for at least 10 minutes before each reading and should be taken before any blood draws. Vital signs should be collected pre-dose on the days of study drug dosing.
- g Optional, to be conducted only at study centres with the appropriate facility to conduct the assessment. There is no requirement for all participants at centres undertaking the sub-study to participate.
- h To be collected prior to study drug administration.
- h Containers to be dispensed at any study visit as required.
- i At specific PK sampling sites, for a sub-group of at least 80 participants (20 per dose group including placebo), 4 additional PK samples will be collected at this visit within 1-2 h, 2-5 h, 5-8 h, and 8-12 h post-dose. Pre-dose samples will be collected for all participants. Each PK sample must be separated by at least 1 h.
- j Only if consent is obtained. The blood sample for Genomic Initiative will be obtained from the participants at Visit 3 prior to study drug administration (at or after randomisation). If for any reason the sample is not drawn at Visit 3, it may be taken at any visit window until the last study visit. Only 1 sample should be collected per participant.

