Appendix D: Exclusion from Per-Protocol Analysis

Participants will be excluded from Per-Protocol analysis if they present with an important protocol deviation (IPD) which is deemed to severely impact the validity of the analysis. The IPDs identified as leading to exclusion from the Per-Protocol analysis set are outlined in the protocol deviation specification. All protocol deviations are reviewed by the study team and IPDs are reviewed on a case-by-case basis.

During the study, prior to the interim analysis and interim database lock, it was documented that one site in Poland (site 5702) did not have sufficient source documentation or medical validation for anomalous laboratory assessments. The data from the site could impact data integrity of the interim and final analyses if included in the Per-Protocol analysis set. A specific IPD was created and documented as:

- Data entered in the eCRF that are transcribed from source documents not being consistent with the source documents and /or the discrepancies are not explained /and /or medical records not available.

Participants from the site in Poland were allocated this IPD and are thereby excluded from the Per-Protocol analysis set. Their data will remain in the Full Analysis Set, in line with the Intention-to-Treat principles.

SIGNATURE PAGE

This is a representation of an electronic record that was signed electronically and this page is the manifestation of the electronic signature

Document Name: d7551c00001-sap-ed-3		
Document Title:	Statistical Analysis Plan Edition 3	
Document ID:	Doc ID-004403347	
Version Label:	5.0 CURRENT LATEST APPROVED	
Server Date (dd-MMM-yyyy HH:mm 'UTC'Z)	Signed by	Meaning of Signature
28-Sep-2022 12:02 UTC	PPD	Content Approval

Notes: (1) Document details as stored in ANGEL, an AstraZeneca document management system.

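### The Per-Protocol repeats of the Week 12 UACR and eGFR analyses require dapagliflozin after Week 12, so they condition a Week 12 result on later events and cannot isolate the effect of protocol deviations

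*SAP*

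**What the plan says.** - **Per-Protocol Population (SAP 4.5, Table 3).** There are two conditions. The first is membership of "A subset of the Full Analysis Population consisting of all participants who receive the additional treatment with dapagliflozin post-Week 12". The second is that participants "do not violate the terms of the protocol in a way that may affect the primary efficacy endpoint significantly"; the primary endpoint is UACR at Week 20.
- **Week 12 UACR (SAP 4.9.3.1).** For the main analysis, "The population of interest are randomised participants who meet all eligibility criteria and have valid non-missing urine ACR records at baseline" and at at least one later visit. No dapagliflozin condition applies. Then: "The analysis will be repeated on the Per-Protocol Analysis Population".
- **Week 12 eGFR (SAP 4.9.3.2).** For the main analysis: "The FAS will be used for this analysis and eGFR will be evaluated on the original scale". The same sentence about a Per-Protocol repeat follows.
- **Who can receive dapagliflozin.** Protocol 4.1 admits to Treatment Period 2 only those still on their assigned treatment. SAP Appendix A, footnote a, adds: "Any participant with urine ACR < 30 mg/g at Week 12 will be excluded from Treatment Period 2". The check at Visit 7 uses the last available UACR. Under Protocol 7.1, those who stop AZD5718 in Period 1 do not go on to Period 2.
- **Use of analysis sets (SAP 4.4.2).** The effect of important deviations is to be examined by comparing results across analysis sets, with and without the affected data.
- **Unverifiable site (SAP Appendix D).** Its participants "are thereby excluded from the Per-Protocol analysis set" but stay in the Full Analysis Set.
- **Termination (SAP 4.14).** It records that "the total number of randomised participants is 613 with 340 participants completing treatment".

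**The concern.** The Week 12 endpoints ask what AZD5718 does before study dapagliflozin is added. Whether someone later takes dapagliflozin is no part of that question, yet it decides who enters the repeat. Three groups can be dropped without having violated anything: those at Visit 7 with UACR under the threshold, those who stopped study drug in Period 1, and those whom termination reached before Period 2. The second condition, tied to Week 20, also lets a deviation between Weeks 12 and 20 delete a valid Week 12 observation.

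At stake is the interpretation of the repeat. If it agrees with the main analysis, that does not show robustness to deviations. If it disagrees, the cause cannot be identified.

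**Working it through.** The plan gives no figure on this point to reproduce, and the power inputs are redacted. The definitions are traced first; the possible sizes follow from stated assumptions.

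**1. What separates the main Week 12 analysis from its repeat**

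| Reason for absence from the repeat | Protocol violation needed? | Timing |
|---|---|---|
| Important deviation up to Week 12 | Yes | By Week 12 |
| Unverifiable site | Assigned a site-specific deviation | Whole study |
| Last available UACR at Visit 7 below 30 mg/g | No | At about Week 12 |
| Stopped study drug in Period 1 | No | Before Week 12 |
| Termination before Period 2 | No | Any time before dapagliflozin |
| Deviation in Weeks 12 to 20 | Yes, but after the endpoint | After Week 12 |

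Only the first two rows belong to a Week 12 deviation question. The other four enter through the Week 20 definition.

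**2. Counts.** 613 − 340 = 273, and 273/613 = 44.5% did not complete treatment. The documents do not say how many of the 273 never started dapagliflozin, or how many of those have a Week 12 value.

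**3. The 30 mg/g threshold.** From the entry range of 200 to 5000 mg/g (Protocol 5.1), reaching 30 mg/g needs a fall of 1 − 30/200 = 85% to 1 − 30/5000 = 99.4%. A simulation assumed a log-normal baseline truncated to 200–5000 mg/g, with geometric mean parameter 400 to 900 mg/g and log SD 0.8 to 0.9. It also assumed an SD of log change of 0.6 to 1.0, a placebo change of −5%, and a true effect of 20% or 30%.
- Removed: 0.0% to 0.7% on placebo and 0.0% to 1.6% on active drug.
- Largest shift in the baseline-adjusted effect: a 30.0% reduction estimated as 28.6%, or 1.4 percentage points towards no effect.

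**4. Other non-entry.** Assume no true effect, an SD of log change of 0.8, a fraction f excluded in each arm, and correlation ρ between exclusion and the Week 12 change. The mean log change among those kept moves by −0.8 × ρ × φ(z)/(1 − f), where z is the (1 − f) normal quantile. With ρ = 0.3 in one arm and 0 in the other:
- f = 0.10: 0.8 × 0.3 × 0.1755/0.90 = 0.047, a spurious difference of about 5%.
- f = 0.20: 0.8 × 0.3 × 0.2800/0.80 = 0.084, a spurious difference of about 8% to 9%.

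The sign depends on which arm carries the correlation. With ρ = 0 in both arms, the difference is zero.

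**5. Precision at Week 12.** Under Protocol 7.1, Period 1 stoppers complete only the Discontinuation and Follow-up Visits. SAP 4.2 does not map the Discontinuation Visit to an analysis visit, and SAP 4.9.1.4 does not impute UACR.
- eGFR: in a by-visit ANCOVA, a person with no Week 12 value is absent from both runs, so removing that person costs nothing at Week 12.
- UACR: such a person informs Week 12 only through earlier visits in the mixed model. With a fraction p lost and correlation r between early and Week 12 change, a two-visit approximation gives a standard-error factor of 1/√(1 − r²p). Assume 25% to 50% of the 273 left in Period 1 (68 to 137 people; 68/613 = 11.1%, 137/613 = 22.3%) and r = 0.4 to 0.8. The rise is then about 1% to 4% for p = 0.111 and 2% to 8% for p = 0.223.

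**The case against.** The strongest reply is that these are supplementary runs of secondary endpoints. The main Week 12 analyses carry no dapagliflozin condition, and SAP 4.14 already urges caution on efficacy after early termination. That stands, and it limits the priority.

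Neither 4.9.3.1 nor 4.9.3.2 calls its repeat a deviation analysis; the purpose comes from the general statement in 4.4.2. That also stands. But no other purpose is given, and no other Week 12 efficacy set is defined.

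The UACR comparison is not simply Full Analysis against Per-Protocol. Its main population already requires eligibility and valid records, so eligibility deviations are out of both runs. Since valid is undefined, it is not certain that the main UACR run keeps the unverifiable site. For eGFR the main set is the Full Analysis Set, which does keep it.

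SAP 4.5 promises exclusions by reason and by-participant listings. These give counts per reason but do not separate the effects on the estimate.

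Excluding people who stop study drug is common in per-protocol sets, so dropping Period 1 stoppers is arguable. If it is wanted, it should be an explicit Period 1 adherence rule, not a by-product of the dapagliflozin condition. It would not justify the other exclusions.

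**Conclusion.** The point holds as a problem of definition: a set built for Week 20 is reused for an earlier question it does not fit. It does not touch the main Week 12 analyses or the Week 20 analyses, where the dapagliflozin condition matches the question.

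The bias is unknown. The ranges above rest on assumed distributions and correlations; non-entry related to outcome differently by arm is the larger risk, and the threshold is minor. The loss of precision at Week 12 is minimal for eGFR and modest for UACR.

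A reader might infer three stronger things that the documents do not support:
- **That 44.5% of participants are lost from the Week 12 repeat.** The 273 include people who stopped in Period 2 after starting dapagliflozin, and the split by period is not given.
- **That standard errors rise by 6% to 13%.** This comes from 1/√(1 − 0.111) = 1.06 and 1/√(1 − 0.223) = 1.13, which treat every Period 1 leaver as supplying a Week 12 value to the main analysis. Most do not.
- **That the threshold always removes the best responders on the Week 12 value.** It is an absolute level, not a change: a fall from 200 to 29 mg/g (85.5%) is removed, while one from 5000 to 100 mg/g (98%) stays. The value checked is also the last available one, which may predate Week 12.

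**What to change.** Add a Week 12 Per-Protocol Population to SAP Table 3: Full Analysis participants with no Per-Protocol-excluding deviation up to Week 12 and not from the site in Appendix D, with no dapagliflozin condition. Add a matching row in SAP 4.5.1 with the data period ending at Week 12; the Monotherapy Safety Analysis Set already does this for safety. Use the new set for the repeat in 4.9.3.1 and for the Week 12 eGFR repeat in 4.9.3.2. Keep the existing Per-Protocol Population for all Week 20 analyses, including the Week 20 eGFR model.

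The cost is one population flag, two re-pointed runs and SAP wording. No new data are needed. SAP 4.12.1 and 4.14 describe the main study team as still blinded, with these analyses to follow database lock, so on the SAP's own account the change could be specified in advance.

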4.5.1 Analysis Sets

Analysis sets consist of two components: (1) analysis population (See Section 4.5), which specifies the participants included in an analysis; (2) data period, defining the time period during which data will be included in the analysis.

Analysis Set	Analysis Population	Data Period
Full Analysis Set	Full Analysis Population	Day 1 to the end of the follow-up period
Per-Protocol Set	Per-Protocol Population	Day 1 to the end of the follow-up period
Safety Analysis Set	Safety Analysis Population	Day 1 to the end of the follow-up period
Monotherapy Safety Analysis Set	Safety Analysis Population	Day 1 to the end of the first treatment period
Extended Safety Analysis Set	Extended Safety Analysis Population	Day 1 to the end of the follow-up period with flag to subset Week 12 to the end of the follow-up period

The Extended Safety Analysis Set includes participants who entered the second treatment period. The Week 12 flag is added to the Extended Safety Analysis Set to allow subsetting of participant data to be from Week 12 to end of study.

